8.5.2. Study Termination

Subjects who discontinue treatment without disease progression or death will continue to be followed for PFS every 6 weeks after the EOT Visit (± 5 days) for the first 8 assessments (ie, through week 48), and then every 8 weeks (± 5 days) thereafter until disease progression, death, start of subsequent anticancer therapy, or withdrawal of consent. After subjects have discontinued treatment because of disease progression, they will be contacted approximately every 12 weeks to assess survival status (OS) and to document receipt of subsequent anticancer therapy unless consent to participate is withdrawn. Subjects will be terminated from the study for the following reasons:

- Death
- Withdrawal of consent
- Loss to follow-up
- Occurrence of 150 OS events
- Sponsor termination of the study

If subjects are terminated from the study because of the occurrence of 150 OS events or Sponsor decision, Sponsor will continue to provide drug to subjects who are benefiting from treatment.

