Post-Treatment Follow-up Visit: A Post-Treatment Follow-Up Visit for safety will occur 28 days (no more than 33 days) after the last dose of study drug. Every effort must be made to perform protocol-specified evaluations unless consent to participate in the study is withdrawn. If a subject's dose is interrupted for 28 days and then the subject discontinues study participation, the EOT Visit will serve as the Post-Treatment Follow-up Visit.

PFS and Survival Follow-up: Subjects who discontinue study treatment for reasons other than disease progression or withdrawal of consent will be followed in PFS follow-up (every 6 weeks through week 48 and every 8 weeks thereafter) until documented disease progression or the initiation of new cancer therapy. If a subject begins a new anticancer therapy during PFS follow-up, information on the new anticancer therapy will be collected.

OS follow-up assessments will occur approximately every 12 weeks after EOT unless the subject is in PFS follow-up at that time. If a subject progresses or does not come back for scans while in PFS follow-up, then the OS follow-up assessments will begin at the next planned OS follow-up time point, following the schedule of every 12 weeks after EOT. OS follow-up will continue until all subjects have died, withdrawn consent, are lost to follow-up, or until the occurrence of 150 OS events, whichever occurs first.

Primary Endpoint Results and Subsequent Study Unblinding: Once the primary endpoint of PFS (based on central radiology RECIST 1.1 assessment) is statistically analyzed, the Sponsor will communicate the topline aggregate results of the study via public disclosure, which will include participating study teams. Shortly after public disclosure of the topline aggregate results, the Sponsor will communicate to all sites that treatment assignments of all subjects will be unblinded and will also inform sites which of the 2 following scenarios to pursue following unblinding.

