Radiographic assessment (CT or MRI) for evaluation of disease response will be conducted every 6 weeks (± 5 days) for the first 8 assessments (ie, through week 48) and every 8 weeks (± 5 days) thereafter from C1D1, independent of dose delays and/or dose interruptions, and/or at any time when progression of disease is suspected. For subjects who discontinue study drug/placebo for reasons other than disease progression or start of another anticancer agent, an assessment will be conducted at the EOT Visit. Upon request by the Investigator, the subjects and site staff will be unblinded to treatment assignment after documented disease progression (as assessed by the Investigator) in consultation with the Sponsor Medical Monitor, and subjects randomized to the placebo arm who continue to meet eligibility criteria determined in the EOT visit will be given the opportunity to cross over to the active treatment arm and receive AG-120. For those subjects who cross over, placebo will not be counted as a prior line of therapy for the purpose of eligibility. If subjects cross over, they will start again with study procedures as at C1D1. These subjects will continue to be evaluated for tumor response by the Investigator. If the treatment assignment is determined to be AG-120 upon radiographic disease progression, the Investigator may consider continuing treatment with AG-120, provided the subject is clinically benefitting and there is no contraindication to continuing treatment beyond progression (see Section 9.8 for parameters for treating beyond progression). Target and non-target lesion selection and objective tumor response assessments per Response Evaluation Criteria in Solid Tumors (RECIST) v1.1 will be performed by the institutional radiologist(s). An independent central review of response will be conducted by an Independent Radiology Center (IRC) per RECIST v1.1. All scans will be sent to the IRC as detailed in the site-specific Imaging Core Manual (see Section 10.7.2).

HRQOL assessments will be conducted pre-dose on C1D1 and on Day 1 of every cycle thereafter until EOT. After EOT visit, the HRQOL will be conducted every 12 weeks until the start of new anticancer therapy. One additional HRQOL assessment will also be conducted at the safety follow-up visit. Health economic outcomes assessments will occur pre-dose on C1D1, C3D1, and at the EOT Visit. Compliance assessments will occur at C1D15, Day 1 of every cycle

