If the primary endpoint is statistically negative, all ongoing AG-120 subjects will be permitted to continue receiving open-label AG-120 following unblinding at the discretion of the treating investigator. Palliative radiotherapy will be allowed for subjects who continue receiving AG-120 as described in the preceding “statistically positive” paragraph. Subjects who were receiving placebo will not be permitted to receive open-label AG-120 in this scenario and will come off study.

Post-Treatment Follow-up Visit: A Post-Treatment Follow-Up Visit for safety will occur 28 days (no more than 33 days) after the last dose of study drug. Every effort must be made to perform protocol-specified evaluations unless consent to participate in the study is withdrawn. Assessments to be performed at the Follow-up Visit include ECOG PS and AE and concomitant medication recording. If a subject’s dose is interrupted for 28 days and then the subject discontinues study participation, the EOT Visit will serve as the Post-Treatment Follow-up Visit.

PFS and Survival Follow-up: Subjects who discontinue study treatment for reasons other than disease progression or withdrawal of consent will be followed in PFS follow-up (every 6 weeks through week 48, and every 8 weeks thereafter) until documented disease progression or the initiation of new cancer therapy. If a subject begins a new anticancer therapy during PFS follow-up, information on the new anticancer therapy will be collected.

OS follow-up assessments will occur approximately every 12 weeks after EOT unless the subject is in PFS follow-up at that time. If a subject progresses or does not come back for scans while in PFS follow-up, then the OS follow-up assessments will begin at the next planned OS follow-up time point, following the schedule of every 12 weeks after EOT. OS follow-up will continue until all subjects have died, withdrawn consent, are lost to follow-up, or until the occurrence of 150 OS events, whichever occurs first.

End of Study: End of study is defined as the point in time when all subjects have died, withdrawn consent, been lost to follow-up, or until 150 OS events have occurred. Final analysis for OS will be conducted at the end of the study.

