- ³ Subjects who discontinue study treatment for reasons other than disease progression or withdrawal of consent will be followed every 6 weeks after the EOT Visit (±5 days) for the first 8 assessments (ie, through week 48), and then every 8 weeks (±5 days) thereafter for radiographic assessments until documented disease progression, death, start of subsequent anticancer therapy, or withdrawal of consent.
- ⁴ Subjects are to remain at the study center for 4 hours following the C1D1 and C2D1 doses for PK/PD and ECG assessments.
- ⁵ Height is to be obtained only at the Screening assessment.
- ⁶ On C1D1 and cross over C1D1, assessment should be conducted pre-dose.
- ⁷ Systolic and diastolic blood pressure, heart rate, respiratory rate, and temperature. Assessments should be conducted while the subject is seated or supine. On C1D1 and cross over C1D1, assessments should be conducted pre-dose.
- ⁸ Procedure is to be conducted at Screening. The same procedure to evaluate LVEF should be conducted thereafter only if clinically indicated.
- ⁹ Subjects will have most recent banked tumor (preferably within the last 3 years) or fresh biopsy samples available for IDH1m confirmation (R132C/L/G/H/S mutation variants tested) by central laboratory prior to receiving their first dose of study treatment (see Section 10.4). This sample can be collected at either Pre-screening or the Screening Visit. At least 100 microns of formalin-fixed paraffin-embedded tissue or a tumor tissue block with corresponding pathology report should be available for shipment to a laboratory designated by the Sponsor. These samples will be subjected to additional exploratory biomarker analyses. Date of tumor tissue collection for either banked or fresh tumor samples should be recorded based on the pathology report. Detailed instructions for tumor tissue collection and shipping for central testing will be provided in a separate lab manual.
- ¹⁰ Hemoglobin, red blood cell (RBC) count, white blood cell (WBC) count and differential (% neutrophils, % bands), and platelet count. No need to repeat on C1D1 if baseline assessment performed within 3 days prior to that date, or on cross over C1D1 if EOT assessment performed within 3 days prior to that date. On C1D1 and cross over C1D1, assessments should be conducted pre-dose.

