²¹ If a subject goes off treatment for reasons other than disease progression, response assessments will be conducted at the EOT Visit and every 6 weeks (± 5 days) for the first 8 assessments (ie, through week 48), and then every 8 weeks (± 5 days) thereafter until withdrawal of consent, disease progression, death, the subject is lost to follow-up, or until the end of study/study termination.

²² EORTC-QLQ-C30, EORTC-QLQ-BIL21, and PGI-S (physical function, appetite loss, and pain) to be conducted pre-dose on C1D1 and cross over C1D1; PGI-C is not collected on C1D1 or cross over C1D1. After EOT visit, the HRQOL will be conducted every 12 weeks until the start of new anticancer therapy.

²³ EQ-5D-5L to be conducted pre-dose on C1D1 and cross over C1D1.

²⁴ For all subjects, plasma samples will be obtained for evaluation of IDH mutations and other genes in circulating tumor DNA at Screening, on C1D15, on Day 1 of every cycle thereafter, and at EOT. No need to repeat on cross over C1D1 if EOT assessment performed within 3 days prior to that date.

²⁵ For all subjects, blood samples must be obtained at Screening, on Day 1 of every cycle thereafter, and at EOT. No need to repeat on cross over C1D1 if EOT assessment performed within 3 days prior to that date.

²⁶ A buccal swab for germ-line mutation analysis will be obtained at Screening.

²⁷ Adverse events will be graded according to the National Cancer Institute Common Terminology Criteria for Adverse Events v4.03. After informed consent has been obtained but prior to initiation of study drug, only serious adverse events (SAEs) caused by a protocol-mandated intervention should be reported. After

initiation of study drug, all AEs and SAEs regardless of attribution will be collected. Any SAEs that are assessed as related to study treatment that occur >28 days post-treatment also are to be reported.

²⁸After a subject discontinues treatment due to progression of disease, they will be contacted every 12 weeks (± 7 days) thereafter for assessment of survival status (OS), HRQOL, and anticancer therapies until death, withdrawal of consent, the subject is lost to follow-up, the occurrence of 150 OS events, or until the end of study/study termination, unless consent to participate is withdrawn.

Table 4: Pharmacokinetic/Pharmacodynamic Sampling (2-HG) and Electrocardiogram Schedule*

Visit/Cycle:	Screening	Cycle 1				Cycle 2		Cycle 3+		EOT ¹		Safety F/U
Study Day:	D -28	D1		D15		D1		D1		D +28		

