10.7. Efficacy Assessments

10.7.1. Response to Treatment

The efficacy of AG-120 will be evaluated by assessing response to treatment according to RECIST v1.1 ([Eisenhauer, et al. 2009](#)) ([Appendix 15.9](#)).

Radiographic assessments (CT or MRI) to obtain tumor measurements are to be conducted at Screening, every 6 weeks for the first 8 assessments (ie, through week 48), and every 8 weeks thereafter (± 5 days) from C1D1, independent of dose-delays and/or dose interruptions, and/or at any time when progression of disease is suspected. CT imaging of the chest, abdomen, and pelvis (Torso) with triphasic IV contrast (30 millisieverts [mSv] per scan) should be performed at baseline and on study. For subjects with allergy to IV iodine contrast, CT of the chest without IV contrast and MRI of the abdomen with IV contrast should be performed at baseline and on study. Brain scans with CT (2 mSv per scan) or MRI should be performed at baseline in subjects with known treated brain metastases and on study at the same imaging time points as Torso imaging. Bone scans (4 mSv per scan) will be performed at baseline if disease is suspected and on study as appropriate as the same imaging time points as Torso imaging. Any ancillary findings on the radiographic assessments will be communicated to the appropriate physician for notification to the subject. The same method (CT or MRI) should be used consistently for any given subject. For subjects randomized to placebo who receive palliative radiotherapy after unblinding and during the cross over period, a repeat CT or MRI will be performed at the end of the 2-week washout period after radiotherapy to document the area that was irradiated and to serve as the new baseline against which all subsequent RECIST v1.1 assessments will be performed, for the purpose of documenting PFS2 during the unblinded open-label cross over period (see [Section 12.12.1](#)). The reading radiologist(s) should be provided the dates and location of the intervening radiation when performing the new baseline assessment. For subjects permitted to continue on open-label AG-120 beyond documented radiographic progression or study unblinding, a new baseline imaging assessment will not be required and the imaging assessments will continue on the current schedule. For subjects who discontinue study drug for reasons other than disease progression, an assessment will be conducted at the EOT Visit and every 6 weeks through week 48, then every 8 weeks thereafter (with the exception of those subjects who initiate a new cancer therapy after discontinuing study treatment) until withdrawal of consent, disease progression, death, the subject is lost to follow-up, or until the end of study/study termination.

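### PFS scans after stopping treatment without progression are counted from the EOT Visit in two places, while the general schedule counts from C1D1 and the other off-treatment text names no anchor

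*Protocol*

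**What the plan says.** The passages fall into three groups.

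- **Counted from EOT.** Section 8.5.2 states that subjects who stop without progression "will continue to be followed for PFS every 6 weeks after the EOT Visit". Table 3 footnote 3 states that they "will be followed every 6 weeks after the EOT Visit". Both then allow eight 6-weekly assessments before 8-weekly scanning begins.
- **Counted from C1D1.** Section 7.1 runs the radiographic schedule "thereafter from C1D1, independent of dose delays and/or dose interruptions", and Section 10.7.1 runs it "from C1D1, independent of dose-delays and/or dose interruptions". The synopsis and SAP Section 4 give the same schedule. This wording covers delays and interruptions and does not mention permanent discontinuation. The SAP gives no other calendar.
- **Off treatment, no anchor.** In the synopsis these subjects "will be followed in PFS follow-up (every 6 weeks through week 48 and every 8 weeks thereafter". Section 7.1 has almost the same sentence: "will be followed in PFS follow-up (every 6 weeks through week 48, and every 8 weeks thereafter". Section 10.7.1 says "an assessment will be conducted at the EOT Visit and every 6 weeks through week 48, then every 8 weeks thereafter". Table 3 footnote 21 says "response assessments will be conducted at the EOT Visit and every 6 weeks", again for eight assessments.

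SAP Table 1 censors a progression or death that follows a gap of at least 95 days from the previous adequate assessment. It sets the censoring date by reference to missed scheduled assessments. Protocol Section 12.7.1 keeps the actual event date after a single missed assessment and censors progression after two or more.

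**The concern.** PFS by IRC is the primary endpoint, and radiographic progression is dated by the scan that shows it. For a subject who stops without progression, the text leaves open whether the next scans follow the C1D1 calendar or a new series from EOT. It also leaves open whether 8-weekly scanning starts at week 48 from C1D1 or 48 weeks after EOT. About 55 centers have to interpret this.

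Two things are at stake. The recorded PD date depends on the calendar in force. Through the SAP's elapsed-time rule, so can the subject's status as an event or a censored observation.

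The EOT anchor is itself loose. Section 7.1 allows the visit up to 33 days after the last dose. Section 9.10.1 defines EOT as the date drug was first held when a toxicity hold becomes permanent.

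**Working it through.** **Inputs.** Scans every 6 weeks for eight assessments, then every 8 weeks, each ±5 days (Sections 7.1, 8.5.2 and Table 3). Censoring gap of 95 days or more (SAP Table 1).

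**1. The plan's own figures.** 8 × 6 = 48 weeks, as stated. This fits either anchor, so it does not show which is meant. The SAP gap is 12 × 7 + 10 = 94 days, so the rule starts at 95.

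**2. The two calendars with EOT at week 20.**

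| Anchor | Scan weeks after EOT | 6-weekly phase ends |
|---|---|---|
| C1D1 | 24, 30, 36, 42, 48, 56, 64, 72 | week 48 |
| EOT | 26, 32, 38, 44, 50, 56, 62, 68, then 76 | week 20 + 48 = 68 |

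**3. Distance between nearest scans, both calendars 6-weekly.** If EOT falls k days after a C1D1-based scan, the nearest scans are min(k, 42 − k) days apart. That ranges from 0 to 21 days. If k is spread evenly over 0 to 41, the mean is 441/42 = 10.5 days. The EOT-based scan day falls within ±5 days of a C1D1-based one for 11 of 42 values of k (26%).

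**4. Effect on a PD date, EOT at week 20.**
- Progression arising between weeks 24 and 26 is dated week 30 on the C1D1 calendar and week 26 on the EOT calendar, so C1D1 is 28 days later.
- Progression arising between weeks 26 and 30 is dated week 30 against week 32, so C1D1 is 14 days earlier.
- With progression spread evenly over those six weeks, the average shift is (2 × 28 − 4 × 14)/6 = 0 days.

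An individual date can therefore move further than 21 days, but in this phase the shifts go both ways and cancel. They do not cancel in the first interval after EOT. There the next C1D1-based scan can come at any point in the interval, while the EOT series waits a full 6 weeks.

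**5. Frequency after week 48 from C1D1.** A subject with EOT at week 60 is scanned 8-weekly at once on the C1D1 reading (64, 72, 80). On the EOT reading the subject is scanned 6-weekly (66, 72, 78) until week 60 + 48 = 108. Mean detection delay is about half the interval: 8/2 = 4 weeks against 6/2 = 3 weeks, a difference of about 1 week.

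**6. Event status.** EOT at week 20, the week-56 scan missed, PD at the next scan:

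| Anchor | Last adequate scan | PD scan | Gap | Under the 95-day rule |
|---|---|---|---|---|
| C1D1 | week 48 | week 64 | 16 × 7 = 112 days | censored |
| EOT | week 50 | week 62 | 12 × 7 = 84 days | event |

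Scan windows do not change this: 112 − 10 = 102 is still at least 95, and 84 + 10 = 94 is still below it. In both rows only one scan was missed, and Protocol Section 12.7.1 would keep the event in both.

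**7. How many subjects.** No planned figure is given. The nearest is the Phase 1 cholangiocarcinoma group in Section 5.3.3.1, where 25 − 19 = 6 of 25 discontinuations were not for progression. Two of the six withdrew consent and would not be scanned, which leaves 4. This is uncontrolled early data and gives a rough scale only.

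**The case against.** The strongest reply is that there is no contradiction. The C1D1 wording is the general schedule, and Section 8.5.2 and footnote 3 are the specific rule for discontinuers. Read in sequence, C1D1 applies on treatment and EOT afterwards. A reader might infer that the protocol also times off-treatment scans from C1D1 outright, so that the two rules cannot both be followed. The documents do not support that: no passage says it. The C1D1 reading comes only from the phrase about week 48, which Sections 7.1 and 10.7.1 define from C1D1 for the general schedule. This part of the reply stands. It does not close the point, because the sequential reading still gives discontinuers a different calendar and, later, a different frequency. A site working from Section 7.1 or 10.7.1 alone could reasonably stay on the C1D1 calendar.

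Second, the censoring trigger is elapsed days, not a count of missed scans, so it needs no anchor to apply. That is correct. Even with the EOT scan missed, the gap to EOT + 6 weeks is at most 41 + 42 = 83 days when EOT is by week 48, or 93 with both windows, which is under 95. The calendar matters indirectly: it fixes when scans occur, and so whether one missed scan takes the gap past 95 days. It also matters for the censoring date, which SAP Table 1 does tie to scheduled assessments.

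Third, the schedule is the same in both arms and treatment is blinded until progression. A scan is required at EOT, and scans are allowed whenever progression is suspected. All of this stands and limits the effect.

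**Conclusion.** The point holds as a gap in the definition of the assessment calendar for the primary endpoint, and it should be corrected. For subjects who stop without progression, two passages count from EOT, the general schedule and the SAP count from C1D1, and the remaining off-treatment text does not say.

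The average effect is small: nearest scans differ by 0 to 21 days in the 6-weekly phase, with shifts in both directions, and mean detection delay differs by about 1 week where one calendar is 6-weekly and the other 8-weekly. The more consequential effect is on status, where one missed scan gives 112 days and censoring on an 8-weekly schedule, against 84 days and an event on a 6-weekly one. That result assumes that the SAP's 95-day rule is applied as written, even where only one scan was missed.

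Two stronger inferences are not supported. A reader might conclude that PD dates are moved systematically by a whole scan interval. That is a bound for an individual subject, approached only when the calendars nearly coincide and progression arises in the short stretch between them. A reader might also conclude that the treatment comparison is biased. That would need stopping without progression to differ by arm, which is possible (for example through adverse events) but is not shown. The share of affected subjects and the effect on the hazard ratio cannot be computed from the documents.

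**What to change.** State one anchor for off-treatment PFS scans and one rule for when 8-weekly scanning starts, identical in both arms. Carry them through the synopsis (radiographic schedule and PFS follow-up), Section 7.1 (the same two places), Section 8.5.2, Section 10.7.1, Table 3 footnotes 3 and 21, and SAP Section 4. The choice of anchor is the sponsor's. If EOT is kept, its date needs a single definition, because Sections 7.1 and 9.10.1 can give different dates.

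In SAP Table 1, name the calendar that defines a scheduled assessment for the censoring date. Also reconcile the 95-day rule in the 8-weekly phase with the single-missed-scan rule in Protocol Section 12.7.1.

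The cost is clarifying text in the protocol and SAP and a note to sites. Sample size, event count, power and alpha do not change.
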